TMS in Primary Progressive Aphasia: Modulation of Brain Networks and Language

NCT Number: NCT04188067

Date: September 9th, 2025

SYNOPSIS

Project title: TMS in Primary Progressive Aphasia: Modulation of Brain Networks and Language

Objective: The objective of this study is to assess the potential transient and durable benefits of repetitive transcranial magnetic stimulation (rTMS) to behavior and brain network in the three variants of Primary Progressive Aphasia (PPA): logopenic, semantic and nonfluent PPA.

Study Period:

Planned enrollment duration: 30 months

Planned study duration: 3 months per participant

Number of Patients: 10

Study Intervention:

Repetitive transcranial magnetic stimulation (rTMS) has emerged as a potential treatment option for Primary Progressive Aphasia. rTMS can induce long-term plastic changes and selectively alter functional network connectivity, which may improve symptoms related to language and cognition. In this study, resting state functional MRI (rsfMRI) is used before rTMS to localize an individually optimized target for stimulation, and after rTMS to measure effects of stimulation on network functional connectivity and language.

Experimental Design:

This study follows a double-blinded, placebo-controlled, cross-over experimental protocol. Participants are randomized to start with either active or sham rTMS during 10 weekdays (Monday through Friday), over 2 consecutive weeks. Intervention arms are separated by a four-week washout period. Language assessments, MRI assessments, and questionnaires are included at the baseline timepoint and after the end of both active and sham arms. A follow-up timepoint including a language assessment is conducted three weeks after the end of Arm 2.

Inclusion criteria:

1. Between the ages of 40-99
2. All participants are native English speakers

3. Willing and able to consent to the protocol and undergo imaging and neuropsychological testing at the specified time points
4. Patients with very mild or mild PPA are included.

Exclusion criteria:

1. History of head trauma involving loss of consciousness or alteration in consciousness
2. Another major neurologic or psychiatric condition
3. Known presence of a structural brain lesion (e.g. tumor, cortical infarct)
4. Any contraindication to MRI, such as presence of pacemakers, aneurysm clips, artificial heart valves, ear implants, metal fragments, or foreign objects in the eyes, skin, or body
5. Longstanding premorbid history (i.e. longer than 10 years) of alcohol or substance abuse with continuous abuse up to and including the time that the symptoms leading to clinical presentation developed
6. Any significant systemic illness or unstable medical condition which could lead to difficulty complying with the study protocol.
7. Unwilling to return for follow-up, undergo neuropsychological testing, TMS, and MR imaging
8. History of unprovoked seizures (i.e., seizures that occur in the absence of a clear provocation such as hyponatremia, hypoglycemia, etc.).
9. Subjects who have a first degree relative (e.g., father, mother or sibling) with a seizure disorder.
10. Subjects currently taking, or plan to take, medications which are highly epileptogenic. These include clozapine, high doses of bupropion (i.e., greater than 400mg daily), diphenhydramine, cyclosporine, isoniazid, imipenem, chloroquine, tramadol and theophylline.
11. Subjects actively on anti-amyloid treatments.

Equipment:

MRI: scans acquired using a Siemens 3.0 T whole-body Siemens MRI scanner housed at the Athinoula A. Martinos Center for Biomedical Imaging at the Massachusetts General Hospital, Charlestown Navy Yard. All MRI scan sessions last 30-60 minutes. During MRI scanning patients lie supine in the MRI machine. Patients' heads are fitted with pillows and cushions to reduce motion artifact and are given earplugs to protect their hearing. Patients are given a "squeeze ball," which they can compress at any time if they are feeling uncomfortable or if they wish to be removed from the scanner. Study staff periodically ask patients if they are feeling well.

MRI sequences include brief localizer scans, field-mapping sequences, high resolution anatomical scans, and functional MRI blood oxygenation level-dependent sequences (BOLD).

TMS: rTMS is administered with a MagPro X100 stimulator (MagVenture, Denmark), using a 70 mm figure-of-eight liquid cooled coil capable of doing active or sham stimulation (e.g. the Cool B65 A/P coil).

The target for rTMS is in the left dorsolateral prefrontal cortex. Accuracy and reproducibility of targeting is achieved with a frameless stereotactic optical tracking neuronavigation system (e.g. Brainsight™ or Localite), which permits real-time monitoring of coil placement and head position. Sham stimulation is delivered to the exact same cortical targets. While no electromagnetic stimulation is delivered during sham, the sounds will approximate active stimulation, and skin electrodes will approximate the sensation of active rTMS.

For all sessions, rTMS is delivered at 80-120% of a patient's resting motor threshold. The resting motor threshold is determined by the minimal stimulus intensity to elicit movement of the contralateral first dorsal interosseous muscle-or to elicit a motor evoked potential (MEP) of at least 50 μ V-on three out of six trials. rTMS is administered in an excitatory pattern as intermittent burst stimulation (iTBS) (bursts of 3 pulses of 50Hz rTMS). Parameters are well within established safety guidelines (Rossi et al. 2009).

Primary outcomes:

Language Performance: The primary outcome is the change in language performance as measured by Boston Naming Test (BNT) before and after TMS.

Brain network connectivity: The main neural outcome measure is the relative change in z-transformed correlation coefficients between regions of the language brain network before and after TMS.

Statistical Analysis:

Language performance: A within-subjects repeated measures ANOVA is used to compare the change in language performance following active rTMS condition versus the sham stimulation condition.

Brain network connectivity: A within-subjects repeated measures ANOVA is used to compare the change in language brain network functional connectivity following active rTMS condition versus the sham stimulation condition.

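### No assessment is listed at the end of washout and the ANOVA names no period term: a benefit that outlasts washout would shrink the contrast, a minor and conservative error

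*Combined protocol and SAP*

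**What the plan says.** All of this is in the synopsis, the only level of detail in the document.

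- **Objective:** "The objective of this study is to assess the potential transient and durable benefits of repetitive transcranial magnetic stimulation". Lasting effect is therefore something the trial hopes to find.
- **Experimental Design, order and length:** "Participants are randomized to start with either active or sham rTMS during 10 weekdays (Monday through Friday), over 2 consecutive weeks". The allocation ratio is not stated.
- **Experimental Design, separation:** "Intervention arms are separated by a four-week washout period".
- **Experimental Design, visits:** "Language assessments, MRI assessments, and questionnaires are included at the baseline timepoint and after the end of both active and sham arms". Then: "A follow-up timepoint including a language assessment is conducted three weeks after the end of Arm 2".
- **Primary outcomes:** "The primary outcome is the change in language performance as measured by Boston Naming Test (BNT) before and after TMS". Connectivity is also defined as a change from before to after TMS. Neither definition says which value is the reference for Arm 2.
- **Statistical Analysis:** "A within-subjects repeated measures ANOVA is used to compare the change in language performance following active rTMS condition", compared with sham. The connectivity sentence has the same form: "A within-subjects repeated measures ANOVA is used to compare the change in language brain network functional connectivity following active rTMS condition". Neither names a period, sequence or carryover term.

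**The concern.** A two-period crossover relies on the first treatment's effect having gone when the second period is measured. This trial also looks for effects that last. If benefit persists in participants who receive active first, their post-sham score is raised and the active-minus-sham contrast shrinks. A small result could then reflect a weak effect or a lasting one.

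The listed visits give little help in separating the two. None falls at the end of washout, and the follow-up comes at different distances from active treatment in the two orders.

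Separately, scores may shift between the two post-arm visits through practice or disease progression. Without a period term, that shift goes into the error and, if the orders are unequal, into the estimate as well.

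**Working it through.** The plan gives no power calculation, so there is no figure of its own to reproduce.

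**1. Timeline from the stated durations.** Arm 1 ends at week 2, Arm 2 starts at week 2 + 4 = 6 and ends at week 8, and follow-up is at week 11. Assessments fall at about weeks 0, 2, 8 and 11, with none at week 6. In active-first participants the post-sham visit is 8 − 2 = 6 weeks after active, and follow-up is 11 − 2 = 9 weeks after. In sham-first participants follow-up is 3 weeks after active.

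**2. Expected contrast with one shared baseline.** Let E be the active effect, c the share of it left at the post-sham visit (assumed), p the share of participants who are active-first, and π the shift from the post-Arm 1 to the post-Arm 2 visit. The baseline cancels within each participant.

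- Active-first contributes E − cE − π.
- Sham-first contributes E + π.
- The plain mean is E(1 − pc) + (1 − 2p)π.

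With π = 0 and p = 0.5, c = 0, 0.25, 0.5 and 1 give 100, 87.5, 75 and 50% of E. At c = 1, p = 0.4 gives 60% and p = 0.6 gives 40%. If E = 0 and orders are balanced, the contrast centres on zero.

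**3. What attenuation does to power (illustrative).** Assume E = 1 SD of the paired difference, n = 10 as 5:5, two-sided 0.05 and a period term (8 df). The SE is √(1/10) = 0.316. Power is 79, 68, 55 and 29% at c = 0, 0.25, 0.5 and 1.

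**4. What the period term does.** It averages the two order means equally, with SE = ½√(1/n₁ + 1/n₂).

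| Orders | SE with term | Power with term | Power without term |
|---|---|---|---|
| 5:5 | 0.316 | 79% | 80% |
| 6:4 | 0.323 | 77% | 80% |
| 7:3 | 0.345 | 72% | 80% |

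The table assumes c = 0 and no period effect, so it shows only the cost. Now assume π = 0.5 SD. At 5:5 without the term, the expected variance of the paired differences rises from 1 to 1 + 0.25 × 10/9 = 1.28. In simulation, rejection under no effect is about 3% without the term and 5% with it, and power is 72% and 79%. At 6:4 without the term, the estimate is off by (1 − 1.2) × 0.5 = −0.1 SD; the term removes this. It does not remove carryover: the adjusted estimate is still E(1 − c/2).

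**5. What a pre-Arm 2 BNT could show.** Compare active-first with sham-first on that score, adjusted for baseline, 5 v 5. A paired-difference SD of 1 with independent visit errors means an error variance of 0.5 per visit. The intraclass correlation (ICC) is assumed to be 0.7 or 0.9.

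- Total variance is 0.5/(1 − ICC) = 1.67 or 5.0.
- Residual variance after adjustment is total × (1 − ICC²) = 0.85 or 0.95.
- SE = √(residual × 0.4 × 7/6) = 0.63 or 0.67, where 7/6 is the expected cost of estimating the slope.
- By simulation the mean 95% half-width is 1.43 or 1.51 SD, and power to detect full persistence of a 1 SD effect is 29 or 26%.

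**6. Change from the pre-Arm 2 score.** With r₄ and r₆ the shares left at 4 and 6 weeks, the contrast at 1:1 is E(1 + (r₄ − r₆)/2). It is unbiased if the residual is constant. Under exponential decay r₄ = c^(4/6), so c = 0.25 or 0.5 gives r₄ = 0.40 or 0.63 and a contrast of about 107% of E in each case. Faster fades overstate more: (0.5, 0.25) gives 112.5% and (0.5, 0) gives 125%.

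**The case against.** The strongest reply is that this is an ordinary crossover with an ordinary safeguard. Attenuation by same-direction carryover affects any two-period design, the plan provides four weeks of washout, and nothing in the documents says how much effect remains. Every size above rests on an assumed c. The error works against the treatment and creates no false positive. All of this stands, and it is why the point is minor.

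It is also fair to say that the extra BNT has a low yield. It measures the residual at about 4 weeks, whereas attenuation depends on the residual at about 6 weeks. A comparison of its SE with that of a persistence estimate from the existing post-arm totals would therefore not be like for like. Durability is not wholly unmeasured either: follow-up gives a 3-week language value in sham-first participants, and active-first participants have values at 6 and 9 weeks. A synopsis may also condense a fuller visit schedule.

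Two stronger readings are tempting. A reader might infer that, without a second baseline, the Arm 2 change is undefined and the primary contrast invalid. The text does not support that: it lists a single baseline timepoint, which is the natural reference for both arms and drops out of the BNT contrast. What is missing is one clarifying sentence. A reader might also infer that the post-Arm 1 value is meant as the Arm 2 reference, which would distort the estimate when the treatment works. The wording does not exclude this, but nothing in it points that way.

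What survives is that the durable-benefit objective has no measurement at the end of washout, and that the period term is absent.

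**Conclusion.** The point holds as a minor one. With a shared baseline and balanced orders, the contrast is unbiased if the active effect has gone by about 6 weeks. Otherwise it is E(1 − pc), which at 1:1 means a loss of at most half, reached only at full persistence. This rests on an assumed c, same-direction carryover, no period shift and, where 1:1 is used, an allocation ratio that the plan does not state. The power figures also assume an effect of 1 SD of the paired difference.

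The documents do not support saying that the trial is biased towards a false positive, that the washout is inadequate, or that a pre-Arm 2 baseline would rescue the primary analysis. The case for change is that two additions are cheap: a period term, which protects precision and, with unequal orders, the estimate; and one short test that bears directly on a stated objective.

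**What to change.** 1. **Period term.** Add it to the repeated measures ANOVA for both BNT and connectivity, and state that the single pre-Arm 1 baseline is the reference for both arms. The cost is one degree of freedom, plus some efficiency if orders are unequal: about 1, 3 and 8 points of power at 5:5, 6:4 and 7:3 if there is no period effect.
2. **BNT before stimulation on the first day of Arm 2**, when participants attend anyway. Report the active-first v sham-first difference, adjusted for baseline, as a descriptive estimate with CI of the residual at about 4 weeks. It should not become the primary reference value, and it must not decide which analysis is used. The cost is about 10 short tests and one more practice exposure, for a wide interval. It adds nothing for connectivity.
3. **One sentence on interpretation.** Say that the primary estimate is attenuated if benefit outlasts washout.

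If a sensitivity analysis of change from the pre-Arm 2 score is added, say that it overstates the effect when the residual fades during Arm 2. A comparison using Arm 1 alone is optional. It avoids carryover, but at about 5 v 5 it has only 26 to 29% power under the same assumptions, so it can only be supportive.

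### Durable benefit is an objective, but no durability analysis is specified, and the one follow-up visit gives a sham-controlled estimate only under assumptions the plan does not state

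*Combined protocol and SAP*

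**What the plan says.** The Objective is to "assess the potential transient and durable benefits of repetitive transcranial magnetic stimulation (rTMS) to behavior and brain network", so durability is claimed for both language and connectivity. Study Intervention adds that "rTMS can induce long-term plastic changes and selectively alter functional network connectivity".

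Under Experimental Design, each participant receives active and sham rTMS in random order, two weeks each. "Intervention arms are separated by a four-week washout period". On visits: "Language assessments, MRI assessments, and questionnaires are included at the baseline timepoint and after the end of both active and sham arms". Then: "A follow-up timepoint including a language assessment is conducted three weeks after the end of Arm 2". That sentence names a language assessment and does not mention MRI. No assessment at the end of the washout is listed.

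Statistical Analysis gives two analyses. For language: "A within-subjects repeated measures ANOVA is used to compare the change in language performance following active rTMS condition versus the sham stimulation condition". For connectivity, the same type of ANOVA is "used to compare the change in language brain network functional connectivity following active rTMS condition versus the sham stimulation condition". Neither lists timepoints, names the follow-up visit, or defines a durability contrast. The primary language outcome is a before-to-after change in the Boston Naming Test. The plan does not say which score is the before value for Arm 2, although only one baseline is listed.

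**The concern.** One half of the objective has no analysis attached to it. The visit that looks designed to supply one comes after every participant has had active treatment, so it has no untreated comparator. Participants differ there only in how long ago active rTMS ended. If the benefit lasts, both orders still carry it and the comparison shows nothing. If it has gone, the comparison also shows nothing.

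There is a related consequence for the primary analysis. If change in both arms is measured from the single baseline, any active effect still present when active-first participants finish sham is subtracted from the active-minus-sham contrast. The plan itself raises the possibility of lasting change, and no planned estimate would show whether that had happened.

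**Working it through.** **Timeline** (weeks from the start of Arm 1; durations from Experimental Design). Arm 1 ends at week 2, Arm 2 starts at 2 + 4 = 6 and ends at 8, and follow-up is at 8 + 3 = 11. Eleven weeks is 77 / 30.44 = 2.5 months, which agrees with "Planned study duration: 3 months per participant". This is the only stated figure the schedule can be checked against; no power basis is given for the 10 patients.

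**Time since active ended.** At follow-up: sham-first 11 − 8 = 3 weeks, active-first 11 − 2 = 9 weeks (8.6 if a 28-day washout is counted from the last Friday of Arm 1). At the post-Arm-2 visit, active-first: 8 − 2 = 6 weeks. Post-arm visits are taken as falling right after each arm, since no delay is stated.

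**What each visit identifies.** Let Ak be the active effect remaining k weeks after active ends, and v the effect of the visit itself (practice, progression), equal in both orders. Effects are assumed additive and equal across periods.

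| Visit | Active-first | Sham-first | Difference |
|---|---|---|---|
| After Arm 1 (week 2) | A0 + v2 | v2 | A0 |
| Before Arm 2 (week 6, not in plan) | A4 + v6 | v6 | A4 |
| After Arm 2 (week 8) | A6 + v8 | A0 + v8 | A6 − A0 |
| Follow-up (week 11) | A9 + v11 | A3 + v11 | A9 − A3 |

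The planned visits therefore identify A0, A6 (the sum of the week-2 and week-8 differences) and A9 − A3. They do not identify A3, A4 or A9 separately. Assuming A9 = 0 identifies A3; assuming nil visit effects identifies both A3 and A9.

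**How much of A3 the follow-up difference shows.** Under an assumed exponential decay, (A3 − A9)/A3 is 88% for a 2-week half-life, 65% for 4 weeks, 50% for 6 weeks, 37% for 9 weeks and 0% for a permanent effect.

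**Primary contrast, single baseline.** Active-first: (A0 + v2) − (A6 + v8). Sham-first: (A0 + v8) − v2. The equal-weight mean is A0 − A6/2, which is 100%, 75% or 50% of A0 if none, half or all of the effect remains at 6 weeks. At an assumed 5 v 5, two-sided 0.05, with a period term (8 df), the effect detectable with 80% power is 1.01 SD of the within-person difference. Power at that A0 is 80%, 56% or 29% in the three cases.

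**Primary contrast, arm-specific baselines.** Active-first: (A0 + v2 − v0) − (A6 + v8 − A4 − v6). Sham-first: (A0 + v8 − v6) − (v2 − v0). The mean is A0 + (A4 − A6)/2. The A6/2 loss therefore depends on which baseline is used.

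**Precision of the durability estimates** (5 v 5 assumed, t on 8 df = 2.306, in change-score SD):

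- A4 from a new week-6 assessment: SE = √(1/5 + 1/5) = 0.632; half-width 2.306 × 0.632 = 1.46; detectable effect 2.02 at 80% power; power 29% at 1.0 SD. At 4 v 6 or 3 v 7 the half-width is 1.49 or 1.59.
- A6 from existing visits, equal correlation between visits: two changes from a shared baseline correlate 0.5, so the variance of their sum is 1 + 1 + 2 × 0.5 = 3; SE = √(3 × 0.4) = 1.095; half-width 2.53; power 13% at 1.0 SD.
- A6 under AR(1) at 0.90 to 0.98 per week, in week-6 change-score SD: variance 2.24 to 2.31 times that of A4; half-width 2.18 to 2.22; power 15%.

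**The case against.** The strongest reply is that a washout normally carries a no-carryover premise. If the effect is gone by 9 weeks, the follow-up difference is a randomised, sham-controlled 3-week effect. That is correct, so a reader who infers that the visit can never give a controlled estimate goes too far. What stands against the reply is that the plan does not state the premise, cannot test it with visit effects free, and assumes an answer to part of the durability question.

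The follow-up also has some value beside A6. If persistence is non-negative and does not increase with time, 0 ≤ A9 ≤ A6, so with D = A3 − A9 the 3-week effect lies between D and D + A6. A zero D is uninformative alone, but not necessarily alongside A6.

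A reader might also infer that a small primary result could not be told apart from a lasting benefit. The documents do not support that. The week-2 difference between orders gives A0 free of carryover, and A6 is estimable from existing visits. The shortfall is in precision and prespecification; the data would exist.

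The text is a synopsis. It does not exclude the follow-up from the ANOVAs or claim that it is sham-controlled; the use of that visit is simply unstated.

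Finally, the gain is modest. A 4-week estimate with half-width 1.46 SD could not separate full persistence from none for an effect of about 1 SD. This is a fair limit on what the fix delivers and the reason to label it exploratory. Nor does the fix remove the carryover loss in the primary contrast.

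**Conclusion.** The point holds as a cheap improvement worth making. Durable benefit is an objective, no analysis of it is specified, and with visit effects allowed the follow-up comparison between orders yields only A9 − A3, which is zero at both extremes. Reading it as a sham-controlled 3-week effect needs either no remaining effect at 9 weeks or nil visit effects.

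The loss of up to half of A0 in the primary contrast is a related carryover problem. It depends on using the single baseline in both arms and on persistence to 6 weeks, which the documents do not quantify. It should not be read as the size of the durability gap.

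The lags and the identifiability results follow from the stated schedule under additive effects that are equal across periods. The precision figures rest on an assumed 5 v 5 split.

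**What to change.** 1. Give the existing language assessment on the first day of Arm 2, before stimulation. Sham-first participants have had no active rTMS by then. Report the between-order difference in change from baseline, with its CI, as the exploratory 4-week durability estimate for language. It also gives direct but imprecise evidence on carryover at the end of the washout. A null does not show that the washout was sufficient, and the result should not be used to choose the primary analysis.
2. State that the primary analysis uses the single pre-Arm-1 baseline for both arms and that the new score is not a second primary baseline. State also that the contrast is then A0 − A6/2 with equal orders.
3. For connectivity, either report the 6-week estimate from the existing MRI visits as exploratory, with its assumptions, or limit the durable claim to language.
4. Report the follow-up by order. State the assumption of no remaining effect at 9 weeks that is needed to read it as sham-controlled, and that a zero difference on its own is not evidence about durability.
5. Add a period term to the primary ANOVA. It removes visit effects but not carryover.

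The cost is one more naming-test exposure per participant, on a day already attended; the 11-week schedule is unchanged. The exposure is the same in both orders, so it does not bias the week-6 comparison, but it precedes the post-Arm-2 measurement. Without a period term, a practice shift p there would move the primary contrast by 0 at 5 v 5, 0.2p at 4 v 6 and 0.4p at 3 v 7; with one, by 0. The period term raises the detectable primary effect from 1.00 to 1.01 SD of the within-person difference at 5 v 5 (1.03 at 4 v 6, 1.10 at 3 v 7). Items 2 to 5 need only analysis text.

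### Does the plan leave it unclear whether connectivity is a primary outcome alongside the Boston Naming Test?

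*Combined protocol and SAP*

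**What the plan says.** All the relevant text is in the synopsis of the combined protocol and SAP.

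- **Primary outcomes section.** The heading is plural, "Primary outcomes", with two entries beneath it. The language entry reads "The primary outcome is the change in language performance as measured by Boston Naming Test (BNT) before and after TMS". The connectivity entry reads "The main neural outcome measure is the relative change in z-transformed correlation coefficients between regions of the language brain network" and does not use the word primary.
- **Objective.** The aim is to "assess the potential transient and durable benefits of repetitive transcranial magnetic stimulation (rTMS) to behavior and brain network". Behaviour and brain network appear side by side, unranked.
- **Study Intervention.** Resting-state MRI is used before stimulation to find the target, and "after rTMS to measure effects of stimulation on network functional connectivity and language".
- **Statistical Analysis.** The same two domain labels return with one analysis each. For language: "A within-subjects repeated measures ANOVA is used to compare the change in language performance following active rTMS condition versus the sham stimulation condition". For connectivity: "A within-subjects repeated measures ANOVA is used to compare the change in language brain network functional connectivity", again active against sham.

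No alpha, sidedness, success rule or multiplicity rule is given. The number of patients is 10, with no effect size, SD or power behind it.

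**The concern.** The heading suggests two primary outcomes, while the definite article in the language entry suggests one. The Objective counts change in either domain as a benefit, so it does not settle the matter.

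The difference would matter if the results disagreed. Suppose connectivity reached significance and naming did not. One reader could cite the heading and report that a primary outcome was met. Another could cite the label and report that the primary outcome was missed, with a neural finding alongside. A plan ought to fix that before the data are seen. If the first description were open to whichever outcome succeeded, there would be two chances at a positive primary result and no stated adjustment. With 10 patients and limited power per test, disagreement between the two outcomes is quite possible.

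**Working it through.** **1. The plan's own figure.** The only sample-size figure is 10 patients. It comes without alpha, power, effect size or SD, so it cannot be reproduced, and nothing stated in the plan depends on how this question is answered.

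**2. The wording side by side.**

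| Place | Language | Connectivity |
|---|---|---|
| Primary outcomes, heading | covered by the plural | covered by the plural |
| Primary outcomes, entry | singular primary label | lead measure of the neural domain |
| Objective | named | named, unranked |
| Statistical Analysis | own ANOVA | own ANOVA |

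Two readings fit. In the first, naming is the sole primary and connectivity is the lead neural measure. In the second, each domain has one lead outcome, which accounts for the plural heading and the parallel analyses. Neither requires that success in one domain may stand in for success in the other. The Objective and Study Intervention sentences say what is studied and what the scans are for; they do not assign endpoint status.

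**3. Error rate under each possible rule.** Assume two-sided 0.05 per test and one test per outcome.

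- Naming is the sole primary: error for the primary claim = 0.05.
- Both must succeed: error is at most 0.05, with no adjustment needed. Joint power falls, for example to 0.80 × 0.80 = 0.64 if the tests are independent.
- Either suffices, independent tests: 1 − (1 − 0.05)² = 1 − 0.9025 = 0.0975.
- Either suffices, bivariate normal test statistics: 0.0907 at correlation 0.5, 0.0704 at 0.9, and 0.05 at 1.

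The excess over 0.05 under the either/or rule is therefore 0 to 0.0475. At independence it equals the chance that connectivity is falsely significant while naming is not: 0.05 × 0.95 = 0.0475. If alpha were 0.01 or 0.10 per test, the independent either/or rate would be 1 − 0.99² = 0.0199 or 1 − 0.90² = 0.19.

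**4. How often the outcomes would disagree.** A paired t-test with n = 10 (9 df, noncentrality d√10) stands in for the two-condition ANOVA, ignoring period and sequence terms. Its power at two-sided 0.05 is 0.293, 0.616 and 0.803 for assumed effects d of 0.5, 0.8 and 1.0 SD. With independent outcomes,

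P(connectivity significant, naming not) = power for connectivity × (1 − power for naming).

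- Both effects 0.5 SD: 0.293 × 0.707 = 0.207.
- Naming null, connectivity 0.5 SD: 0.293 × 0.95 = 0.278.
- Naming null, connectivity 0.8 SD: 0.616 × 0.95 = 0.585.

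These cases assume a real connectivity effect, so the significant connectivity result is a true positive. They show that disagreement can happen, but they do not measure error. The documents give no effect sizes or correlation with which to choose among them.

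**5. What a formal choice would cost.** With naming as sole primary, neither analysis loses power. With two primaries at 0.025 each, family-wise error is 1 − 0.975² = 0.0494 if independent, and power per test falls to 0.192, 0.475 and 0.682 at the same three effects.

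**The case for a change.** The strongest argument for acting is that a hierarchy costs one sentence and leaves visits, sample size and both ANOVAs untouched. The reading of one lead outcome per domain does not fully close the gap: it makes connectivity primary in some sense, although the definite article is given only to naming, and it leaves open what counts as overall success. Because the Objective speaks of benefits to the brain network, a connectivity change might also be presented as benefit to patients when naming had not improved.

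Part of this stands. No sentence ranks the outcomes, and a ranking would make the text tidier. But the case has to suppose an either/or success rule that the plan does not contain. The language entry already tells the reader which outcome carries the primary label, and the connectivity entry says plainly that its measure is neural. A report that gives both results under those labels misleads nobody. The worry about the word benefit concerns how a neural finding is interpreted, which is a different matter from which outcome is primary.

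**Conclusion.** The wording is ambiguous, not contradictory, and analysts can fill the gap sensibly by reporting naming as the primary outcome and connectivity as the lead neural outcome, each from its own ANOVA. No stated figure or analysis is wrong under any plausible reading, and the choice between one primary and two belongs to the sponsor, so no change to the plan is called for.

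The size is zero excess error if naming alone is primary or both must succeed. It is 0 to 4.75 percentage points if either result alone could be claimed. That range assumes two-sided 0.05 per test and one test per outcome. If connectivity were tested separately for each pair of regions, the 9.75% ceiling would no longer hold, but that is a separate question from the labels.
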